#### *Safety Population*

The Safety population will be comprised of all subjects who had Dilapan-S® inserted and were randomized. This population will be used for the analysis of safety of the outpatient versus inpatient management. Subjects who were consented and had Dilapan-S® inserted, but not randomized, and had complications attributed to the device will be reported as AEs (detailed in section 9.1).

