**Randomization** will be performed using a computer-generated random list of numbers assigning subjects to the 2 groups of the study. This list of random number assignments will be kept secure in an opaque envelope until the end of the study. 2 randomization sequences will be required for UTMB and CUMC sites.

No significant adverse effects are expected with the use of Dilapan-S® for mechanical dilation as an outpatient when compared to inpatient setting. The most common adverse events from cervical ripening with mechanical dilators such as the Foley balloon have been reported to be less than 1% (8), the most common being pain (0.26%), unintended amniotomy (0.04%), vaginal bleeding (0.07%), non-reassuring fetal heart tracing (0.07%), and uterine tachysystole (too low to quantify). Our group also reported the following adverse effects with inpatient use of Dilapan-S® for cervical ripening in a group of 444 subjects (9):

Maternal and neonatal adverse events	Nr. of cases (%)	Comments (n)
Uterine tachysystole	1 (0.2)	
Non reassuring fetal heart rate	1 (0.2)	
Maternal complications/discomfort	15 (3.4)	Bleeding during insertion/extraction of dilators (12), Cramping/pain (1), Other (1)
Uterine contractions	111 (25)	Tocography during cervical ripening showed low frequency and mild intensity contractions
Maternal infection	14 (3.2)	Chorioamnionitis (9), Urinary tract infection (3), Endomyometritis (1), Wound infection (1)

NICU admission	6 (1.4)	Meconium aspiration (2), Growth restriction (2), Asphyxia (1), Congenital cardiac abnormality (1)
Neonatal infection	1 (0.2)	Neonatal sepsis (maternal group B Streptococcus was not observed prior IOL)

The most significant potential risks noted with Dilapan-S® occur during or shortly after insertion and include vaginal bleeding due to cervical trauma and incidental rupture of membranes, as well as pain or discomfort with placement. If these occur and are persistent (i.e. unresolved pain despite analgesia), subjects will be admitted for delivery (as they require maternal monitoring) and will not be randomized, since they do not fulfill the eligibility criteria to receive the outpatient intervention.

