### **5.3. Randomization**

After Dilapan-S® placement, and if the subject remains eligible, subject will be randomized to the outpatient group or the inpatient group. A confidential computer-generated simple randomization scheme will be prepared and provided by independent vendor (PharmTest, s.r.o., Czech Republic) to our study coordinator. The currently used randomization code will be replaced by 2 randomization codes, 1 of them for CUMC site (both clinics will use the same randomization sequence. The randomization envelopes to be used at CUMC will be provided by UTMB).

A randomization log with group assignment, subject name, and medical record *number* will be used to track the randomization process. The subject will be included in the analysis by intent-to-treat once the randomization assignment has been made.

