### **6.2. Secondary Outcomes**

- Rate of vaginal deliveries (%)
- Rate of vaginal deliveries within 24 hours since admission to hospital (%)
- Rate of vaginal deliveries within 36 hours since admission to hospital (%)
- Time from hospital admission to reach active stage of labor defined as  $\geq 6$  cm (mins)
- Time from device placement to reach active stage of labor defined as  $\geq 6$  cm (mins)

- Change in Bishop score from insertion to extraction of device
- Change in cervical dilation after Dilapan-S®
- Rate of spontaneous vaginal deliveries after one round of cervical ripening (%) (no additional medical or mechanical interventions)
- Rate of operative vaginal deliveries (%)
- Rate of caesarean deliveries (%)
- Rate of artificial rupture of membranes (AROM) (%)
- Rate of epidural analgesia (%)
- Total duration of Dilapan-S® application (insertion to removal/extraction) (mins)
- Device placement to delivery interval (mins)
- Induction (Oxytocin/Prostaglandin initiation) to delivery interval (mins)
- Analgesia used during device placement (%), cervical ripening (%) and labor induction (%)
- Rate of adverse neonatal outcomes (composite and individual) –Apgar score <7 at 1-5-10 minutes, Cord arterial pH <7.1, neonatal ICU admission (%)
- Occurrence of maternal and neonatal complications within 2 weeks after delivery (%)
- Total duration of maternal hospital stay (hours)
- Subject reported clinical outcomes (sleep, rest, pain, activities of daily living, etc.) (Appendix 3)
- Subject reported satisfaction with Dilapan-S® treatment (Appendix 3)
- Medicaid charges for each hospitalized subject in both arms

*(Blood Bank Transfusion Operations, Chemistry Division, Hematopathology Division, JSH Labor & Delivery unit, Materials Management, Microbiology Division, Mother Baby Unit, Pharmacy, Respiratory Care Services, Surgical Operating Suite)*

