**Reporting**

The collection of AEs begins at the time the subject is enrolled into the study (eligible subject with signed informed consent).

Reporting will be done in written via the attached Safety Report Form (Appendix 4).

The Investigator is obligated to send the applicable report to the Sponsor within 24 hours of becoming aware of the event to ensure the safety of all participants in the study and to meet regulatory reporting requirements.

Subsequent reporting to the IRB and the corresponding regulatory authorities will be organized by the Sponsor and in accordance with all applicable legal requirements of the concerned country.

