**Appendix 4:**  
Safety Report Form

Research Protocol # 18-0132		Safety Report Form	

Forward completed information to:          MEDICEM Technology, [name]          e-mail: [contact]      [contact]
			
A. REPORTER (Physician, Nurse, Hospital, Other)			
1. Date of this Report: (dd-mmm-yyyy) - - - - -	2. Name:		
3. Address:			
4. Contact e-mail:	5. Contact Phone:		
B. PATIENT INFORMATION			
1. Subject ID: ..... or  Not Applicable	2. Year of Birth: (yyy) - - - -		
C. ADVERSE EVENT or PRODUCT PROBLEM			
1.  Adverse Event and/or  Product Problem (Device Deficiency)			
2. Outcome Attributed to Adverse Event (Check all that apply)  Death, incl. date: - - - - - (dd-mmm-yyyy)  Life-Threatening  Disability or Permanent Damage  Hospitalization (initial or prolonged)  Congenital Anomaly/Birth Defects  Required Intervention to Prevent Permanent Impairment/Damage			
3. Date of Event Onset: (dd-mmm-yyyy) - - - - -	4. This Report is:  Initial  Follow-Up		
5. Event or Problem Description (Narrative):     			
6. Other Relevant History, incl. Pre-existing Medical Conditions:   			
7. The Event or Problem Occurred:  Before Application  During Application  After Application			
8. Relationship to the Used Device: (only one option to be ticked)  Related (probably or possibly)  Not Related  Not possible to determine			
D. SUSPECTED MEDICAL DEVICE			
1. Product Name:	2. Lot #:		
3. Date of Expiration: (dd-mmm-yyyy) - - - - -	4. Date of Use: (dd-mmm-yyyy) - - - - -		
5. The Suspected Medical Device is being returned:  YES  NO			
DO NOT COMPLETE!			
E. SAFETY REPORT FORM RECEIPT (to be completed by Sponsor only)			
1. Date of Receipt: (dd-mmm-yyyy) - - - - -	2. Name:		
3. E-mail:	4. Phone:		
5. Report Reference:

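### The outpatient-versus-inpatient safety comparison does not exclude adverse events from before randomisation, and analgesia at placement, a pre-randomisation variable, is listed as an outcome to be tested between arms

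*Combined protocol and SAP*

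**What the plan says.** Sections 5.1 to 5.4.1 set the order: consent, insertion, at least 30 minutes of observation, then allocation. Section 5.3 states: "After Dilapan-S® placement, and if the subject remains eligible, subject will be randomized to the outpatient group or the inpatient group". Consent may be taken at an antenatal office visit (Section 5.1).

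On safety data, Section 10.1 says: "The collection of AEs begins at the time the subject is enrolled into the study (eligible subject with signed informed consent". Section 3 includes complications of placement among the data collected. Section 13.1 defines the analysis set, "The Safety population will be comprised of all subjects who had Dilapan-S® inserted and were randomized", and its use, "This population will be used for the analysis of safety of the outpatient versus inpatient management". It adds that device-attributed complications in women inserted but not randomised will be reported as adverse events.

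On timing of risk, Section 3 says: "The most significant potential risks noted with Dilapan-S® occur during or shortly after insertion". It then limits who goes forward: "If these occur and are persistent (i.e. unresolved pain despite analgesia), subjects will be admitted for delivery", and these women are not randomised. Sections 5.2 and 5.4.1 add further grounds for not randomising.

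Section 6.2 lists "Analgesia used during device placement (%), cervical ripening (%) and labor induction" among the secondary outcomes. Section 13.3 analyses nominal variables like the primary outcome, that is, by a chi-square test of the difference in proportions (Section 13.2).

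The Safety Report Form (Appendix 4) asks for "3. Date of Event Onset: (dd-mmm-yyyy", a date without a clock time, and for a tick against before, during or after application.

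**The concern.** An event that happens before allocation has the same expected frequency in both arms, whatever the setting does later. Counting it adds an equal background to both arms. A real excess of events during outpatient ripening would then look smaller in relative terms and be harder to detect. That is the unwelcome direction for a trial that hopes, in Section 12, to show a shorter stay with no cost to mother or baby.

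Placement analgesia raises a different issue. It is fixed before allocation, so a between-arm test of it can reveal nothing about the setting.

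**Working it through.** **1. The plan's own figure.** Section 13.4 gives 54% versus 37.8%, two-sided alpha 0.05 and 85% power. With pooled variance under the null, n = [1.960·√(2·0.459·0.541) + 1.036·√(0.54·0.46 + 0.378·0.622)]² / 0.162² = 168.3, so 169 per arm. Then 169/0.90 = 187.8, so 188. Both figures reproduce, and this point does not touch them. There is no corresponding calculation for safety. The checks below use 188 per arm.

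**2. Can insertion events reach the arm comparison?** Collection starts at consent, insertion precedes allocation, and the safety set is all inserted and randomised women with no start time for events. Section 3 withholds randomisation for events that persist, Section 5.2 for significant bleeding or intractable pain among other reasons, and Section 5.4.1 for contraindications such as active bleeding, ruptured membranes, tachysystole or non-reassuring testing. What can remain is an event that resolved before allocation, such as brief bleeding or pain.

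**3. How many?** The table in Section 3 gives 12 bleeds at insertion or extraction in 444 women. Extraction falls after randomisation and the split is not given, so I take all, half or a quarter as insertion events: 12/444 = 2.70%, 6/444 = 1.35%, 3/444 = 0.68%. Multiplied by 188, that is 5.1, 2.5 or 1.3 events per arm, before allowing for the screening in step 2.

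**4. Effect on an any-event comparison.** Let p0 be the risk of an insertion event, equal in both arms and independent of later events. Let a and b be the later risks in the inpatient and outpatient arms. Each observed risk is 1 − (1 − p0)(1 − later risk), so the risk difference becomes (1 − p0)(b − a). The documents give no rates by setting. I assume a = 5% and b = 10%. The 10% value of p0 is also an assumption, to show the range. Power is for a two-sided 0.05 test of two proportions.

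| p0 | Inpatient | Outpatient | Risk ratio | Difference (points) | Power, 188 per arm |
|---|---|---|---|---|---|
| 0 | 5.00% | 10.00% | 2.00 | 5.00 | 45% |
| 0.68% | 5.64% | 10.61% | 1.88 | 4.97 | 42% |
| 1.35% | 6.28% | 11.22% | 1.78 | 4.93 | 39% |
| 2.70% | 7.57% | 12.43% | 1.64 | 4.86 | 35% |
| 10% | 14.50% | 19.00% | 1.31 | 4.50 | 21% |

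**5. Sensitivity to what counts as a later event.** Take only tachysystole, non-reassuring heart rate and cramping or pain (3 of 444), and assume that the outpatient setting triples them. With i insertion bleeds per 444 women, simply added, the ratio is (i + 9)/(i + 3): 1.40, 1.67 or 2.00 for i = 12, 6 or 3, against 3.00 with none. The difference is 6/444 = 1.35 points throughout. If the 14 maternal infections in the same table also count and are tripled, the ratio is (i + 51)/(i + 17): 2.17, 2.48 or 2.70.

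**6. Analgesia.** Section 6.2 gives three percentages, one per phase. Placement analgesia precedes allocation, so its true arm difference is zero, and a test at 0.05 would flag about 1 comparison in 20 by chance. The ripening and labour percentages do not contain it.

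**The case against.** The strongest reply is that the plan nowhere says insertion events will be counted. Section 13.1 defines which women are analysed, not which events, and Section 10.1 sets when collection starts, not the analysis window. Section 13 calls itself basic principles and leaves detail to a SAP. Section 6.2 lists no pooled any-event rate. Its neonatal items and its complications within two weeks after delivery are not insertion events. The planned test concerns a difference in proportions, which barely moves. Screening removes the worst insertion events, and power to compare rare events is low in any case.

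Most of this stands, and it sets the limits of the point. A reader might infer that the plan prescribes pooling. It does not; it leaves pooling open. A reader might also infer that the whole analgesia comparison is diluted. It is not, because it is reported by phase. And a reader might take 1.4 from step 5 as the expected ratio. That figure rests on an assumed tripling, treats every bleed as an insertion bleed, and leaves out later events such as infections.

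It would also go too far to say that timing cannot be recovered. Appendix 4 has a narrative field and serves as a notification form to the sponsor. Charts and separate data collection forms feed the analysis, and Section 3 names placement and ripening complications separately and records the time of placement.

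The objection does not remove the gap. Section 3 names adverse events as something to compare, and Section 13.1 assigns a population to that comparison with no start time. A later SAP can add the rule, but the safety form asks for no clock time of onset and no before-or-after-randomisation marker, so applying the rule would depend on what narratives and charts happen to hold. Section 6.2 read with Section 13.3 does call for a test of placement analgesia.

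**Conclusion.** The point holds in a limited form. As written, the plan allows transient insertion events into the comparison of settings. The consequence is a risk ratio nearer 1 and lower power, with little change in the risk difference. With assumed later rates of 5% and 10%, insertion risks of 0.68% to 2.70% bring the ratio from 2.00 to between 1.88 and 1.64, and power from 45% to between 42% and 35%. The difference stays within 0.14 points of 5.00. The later rates are assumptions, the insertion share of the 12 bleeds is unknown, and screening before randomisation probably puts the trial toward the smaller end.

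Placement analgesia is misclassified as an outcome, and that conclusion needs no assumption about rates. Ripening and labour analgesia, the neonatal outcomes, the primary outcome and the sample size are untouched. The change is worth making because it is cheap and because any masking would favour a finding of no safety difference.

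**What to change.** - State in Section 13.1 and in the SAP that between-arm adverse event counts include only events with onset after randomisation.
- Report events from insertion to randomisation separately and descriptively, over all women in whom insertion was attempted, including those not randomised. Section 13.1 now provides for women inserted but not randomised; this would also cover failed attempts.
- Move analgesia during placement from Section 6.2 to the baseline table, with no between-arm test. Keep the ripening and labour percentages as outcomes.
- Record clock time of onset, or a before/after randomisation tick, on the data collection form or in Appendix 4. If the tick is not used, the time of randomisation must be recorded too.

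The cost is a few sentences and at most one or two form fields. The drawback is that fewer events remain in the arm comparison, so its estimate will be less precise relative to the event rate.

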#### *Intent-to-treat Population (ITT)*

ITT includes all patients that were randomized into the study and primary outcome has been obtained. ITT subjects will be analyzed in accordance with their randomized study treatment (i.e. in the treatment group they were originally allocated, regardless of treatment actually received). ITT will be used for evaluation of the baseline characteristics and as the primary population for efficacy assessments. Other predefined subgroup interaction analysis for cervical dilation at randomization, parity ( $P=0$  vs  $P>0$ ), or  $BMI > 30 \text{ kg/m}^2$  will be also performed.

#### *Per Protocol Population (PP)*

PP is a subset of ITT patients without any major protocol violation affecting the efficacy endpoints. Major protocol violations include:

1. Treatment assignment error
2. Violation of one or more inclusion/exclusion criteria
3. Use of forbidden medication
4. Premature withdrawal
5. Missing data for the evaluation of the primary endpoint

This list can be extended based on a knowledge of other serious issues appearing in the data.

PP population will be used for assessment of primary endpoint.

### **13.2. Analysis of primary outcome**

Primary outcome of the study is the rate of hospital stay longer than 48 hours. Proportion of patients in the outpatient and inpatient group will be calculated and their difference will be tested by chi-square test by ITT analysis.

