## 3. Concise Summary of Project

The **target population** for our study is women who present for induction of labor. If there is a decision by the obstetrical team to place a mechanical dilator for cervical ripening, the obstetrical team will notify the research staff so that the patient may be screened for the study. If the subject is eligible for the trial, written informed consent will be obtained by person-to-person contact. The PI, study coordinator, or a collaborator will be responsible for the informed consent procedure. After informed consent is obtained and Dilapan-S® is placed, the patient will be randomized to the Outpatient or the Inpatient group. Those randomized to the outpatient group will be asked to come back within 12 hours or sooner if contractions or other conditions arise.

Our **primary objective** will be to compare the hospital length of stay in the inpatient setting to the outpatient setting.

**Secondary objectives** will be to compare other clinical outcomes such as composite maternal and neonatal outcomes, vaginal delivery rate within 24 and 36 hours after admission, time to reach active stage of labor defined as  $\geq 6$  cm, change in Bishop score, rates of spontaneous and operative vaginal delivery, rate of cesarean delivery, adverse events, healthcare cost impact and subject satisfaction.

**Healthcare cost impact** will be assessed based on direct hospital costs or Medicaid charges, using cost minimization technique. In cost-minimization analysis, two or more interventions that have been assumed or shown to have the same effectiveness are compared for cost and the least expensive one is recommended from an economic perspective. The primary analysis will be performed for all those randomized including the costs/charges after randomization. A secondary analysis will be performed accounting separately for costs/charges before randomization.

**Secondary Analysis/ Metanalysis** will be performed for all those randomized as individual participant data meta-analysis all data from respective randomized controlled trials in the different centers, including from UTMB, will be de-identified. All centers will be requested to send the raw data for secondary analysis in an individual participant data meta-analysis. Research groups who share data will get the opportunity of a co-authorship in relation to the size of their study.

Data will be shared in a file that is encrypted and deidentified and password protected.

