## **6. Study Outcomes**

### **6.1. Primary Outcomes**

Rate of hospital stay longer than 48 hours (from admission to discharge)

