### **13.4. Sample size**

Sample size was calculated based on the determination of superiority. The primary outcome is proportion of women with hospital stay >48 hours. For the sample size calculation, we assumed the proportion in the control arm would be 54% ( $p_i = 0.54$ ). This is based on current experience at UTMB and unpublished data from an international registry trial (9). We estimate that outpatient intervention would decrease this proportion by 30% ( $p_{ii} = 0.378$ ). Based on 85% power and two-sided alpha of 0.05, the total sample size per group required would be 169. Accounting for 10% of premature terminations or drop outs the sample size per group becomes 188, making the total sample size needed 376.

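### The primary objective is length of stay, but hours of stay has no confirmatory test, effect estimate or confidence interval; it should be the single key secondary outcome

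*Combined protocol and SAP*

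**What the plan says.** Section 3 says that the primary objective "will be to compare the hospital length of stay in the inpatient setting to the outpatient setting". It names no threshold. Section 12 describes the potential benefit as a shorter stay, which may in turn reduce cost and workload.

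Section 6.1 defines the primary outcome as the rate of stay over 48 h, counted from admission to discharge. Section 13.2 repeats it ("Primary outcome of the study is the rate of hospital stay longer than 48 hours") and says of the two proportions that "their difference will be tested by chi-square test by ITT analysis". Section 13.4 sizes the trial on the same rate: "Based on 85% power and two-sided alpha of 0.05, the total sample size per group required would be 169".

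Total maternal stay in hours appears in section 6.2 as one of 22 bulleted secondary outcomes, with no ranking. For continuous outcomes, section 13.3 gives descriptive summaries by arm and a t-test or Wilcoxon-Mann-Whitney test as appropriate. It specifies no between-arm estimate, confidence interval, testing order or multiplicity rule. The opening of section 13 leaves further detail to a SAP to be approved before database lock.

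**The concern.** The question in section 3 is about duration, and the primary analysis answers a narrower one: how many women cross 48 h. The sections available for review give no reason for that cut; section 13.4 gives only the expected rate above it.

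The mechanism suggests an effect across the whole distribution. Outpatients are told to return 12 h after insertion, or earlier if needed, and are admitted then (5.4.1). Inpatients spend the ripening period in hospital (5.4.2). A stay that falls from 72 to 60 h, or from 46 to 34 h, does not change the primary outcome.

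Two things are at stake. The primary result gives no estimate of hours saved, although the objective and the benefit in section 12 are expressed as length of stay. And because hours sits unranked among many secondary outcomes, even a clear result there would be exploratory.

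**Working it through.** **1. The plan's own figure.** Inputs from section 13.4: "we assumed the proportion in the control arm would be 54" per cent; "We estimate that outpatient intervention would decrease this proportion by 30" per cent, so 0.54 × 0.70 = 0.378; two-sided alpha 0.05; power 85%.

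n = [z₀.₉₇₅·√(2p̄(1−p̄)) + z₀.₈₅·√(p₁(1−p₁) + p₂(1−p₂))]² / (p₁−p₂)², with p̄ = 0.459.

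- First term: 1.960 × √0.4966 = 1.381
- Second term: 1.036 × √0.4835 = 0.721
- n = (2.102)² / (0.162)² = 4.418 / 0.02624 = 168.4, rounded up to 169
- 169 / 0.9 = 187.8, rounded up to 188; total 376

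The figures reproduce. Power at 169 per group is Φ[(0.162 × 13 − 1.381) / 0.695] = Φ(1.04) = 85.1%. At 188 it is 88.6%.

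**2. What the two proportions say about hours.** If stay is normal and the effect is a pure shift, the shift is z(0.54) − z(0.378) = 0.100 + 0.311 = 0.411 SD. The documents give no SD, so the hours are undetermined:

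- SD 20 h: 0.411 × 20 = 8.2 h
- SD 29 h: 0.411 × 29 = 11.9 h
- Effect confined to stays near 48 h, SD 20 h: a mean difference of about 2 h

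All three give 54% against 37.8%, so the primary outcome cannot tell them apart.

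**3. Power of a rank test on hours.** Each simulated distribution was fixed at 54% and 37.8% above 48 h, with 169 per group and 4,000 to 10,000 replicates. All shapes are assumptions.

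| Assumed shape | Chi-square | Wilcoxon | Difference (points) |
|---|---|---|---|
| Normal shift | 86.3% | 95.9% | +9.6 |
| Lognormal (sdlog 0.5) | 85.7% | 96.3% | +10.6 |
| Logistic shift | 85.8% | 93.5% | +7.7 |
| Proportional hazards | 85.5% | 95.3% | +9.8 |
| Gamma, shape 4 | 85.5% | 97.8% | +12.3 |
| Gamma, shape 1.5 | 85.5% | 99.4% | +13.9 |
| 25% longer stays (+30 h) | 85.6% | 96.3% | +10.7 |
| Normal, 24 h discharge blocks | 86.3% | 94.7% | +8.4 |
| Logistic, 24 h discharge blocks | 86.0% | 90.4% | +4.4 |
| Mixture with long stays not shifted | 85.9% | 90.2% | +4.3 |
| t with 3 df | 85.5% | 90.2% | +4.7 |
| Laplace shift (sharply peaked) | 86.5% | 81.6% | −4.9 |
| Effect only near 48 h (SD 20 h) | 86.2% | 21.9% | −64.3 |

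A separate 10,000-replicate run put the logistic gain at about 7 points. Other mixtures with unshifted long stays gave about 7 (85.7% against 92.5%) and about 9 (86% against 95%). At 188 per group the smooth-shift gain is about 6 to 10 points, because the chi-square starts from about 89%.

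**The case against.** The strongest reply is that nothing here is an error. Sections 6.1, 13.2 and 13.4 use one endpoint consistently, the sample size reproduces, and a threshold rate is a legitimate way to make length of stay operational. That stands. A reader might infer that the primary endpoint contradicts the objective or leaves the trial underpowered; the documents support neither reading.

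Next, hours is not discarded. Section 13.3 already yields means, medians and a test, and a difference can be read from the summaries. That also stands; what is missing is rank, a specified estimate and an interval.

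A reader might also take the power loss as a fixed cost of about 10 points, or conclude that a rank test wins under any shift. Neither follows. The size depends on a distribution that the documents do not give, and the Laplace case is a shift of the whole distribution in which the rank test loses. An effect confined near 48 h fits poorly with later admission of nearly all outpatients, but a sharply peaked distribution cannot be excluded.

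Finally, a reader might conclude that hours should replace the 48 h rate as primary. Section 5.3 refers to a randomization code already in use, so the trial was under way. Staff know where each woman ripens, and under section 5.5 the investigators review and validate outcomes. It would be hard to show that such a switch was made without knowledge of outcomes by arm, and the existing primary test already has 85% power. The case for switching is not made.

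**Conclusion.** The point holds as a gap between objective and analysis, and correcting it is an inexpensive improvement. As written, the trial can show that fewer women stay beyond 48 h, but it has no confirmatory route to a statement about hours and no planned estimate or interval for them. That conclusion needs no distributional assumption.

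The power comparison is secondary and conditional: roughly 7 to 14 points in favour of a rank test at 169 per group under common smooth shifts, about 4 to 5 under some heavy-tailed, heaped or mixed shapes, and negative if stays are sharply peaked or the effect sits near 48 h. It should not be quoted as a single figure.

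**What to change.** Keep the rate of stay over 48 h as the primary outcome, and leave the section 13.4 calculation as it is. Make these changes before database lock and before any comparison by arm:

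- **Section 6.2:** name total maternal stay in hours as the single key secondary outcome.
- **Section 13.3:** test it only if the primary test is significant, in fixed sequence at two-sided 0.05, by the Wilcoxon-Mann-Whitney test rather than a choice between two tests. Report the Hodges-Lehmann difference in hours with a 95% CI.
- **Sensitivity analysis:** give women without the outcome the worst rank. This matches section 13.1, where the All Randomized worst-case analysis counts them as having reached the primary outcome.
- **Other secondary outcomes:** state that they are exploratory.

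The cost is a wording change and a registry update, with a dated record that no outcomes by arm had been examined. No new patients, data or procedures are needed.

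The limitation is that hours becomes confirmatory only if the 48 h test succeeds. Under the plan's assumptions at 169 per group, the chance of a confirmatory hours result therefore cannot exceed about 85%. The change supplies the missing estimate and its confirmatory standing; it does not recover the rank test's possible extra power.
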